1.1.2 Oligometastatic disease with long anticipated life expectancy

An oligometastatic state is considered a transitional state between localized and widespread systemic disease,⁶ and though variably construed, is typically defined as patients with <4 metastatic lesions. Although some investigators hypothesize that these patients may still be curable, at the very least data support that these patients have life expectancies that are long, typically median survivals greater than 1-2 years.^{7,8} With standard EBRT dosing among patients with longer life expectancies, there is a very real risk of local recurrence that can cause significant morbidity. In studies evaluating all patients with bone metastases, the median survival is approximately 9 months.³ In patients with oligometastatic disease whose life expectancy surpasses this, local recurrence can be a source of significant morbidity. In a subgroup analysis of the Dutch Bone Metastasis Study specifically looking at patients who survived for longer than a year, around half of patients treated with EBRT for symptomatic bone metastases had progressive pain at a mean duration of 17-18 weeks from radiation.⁹ As these patients are living longer, local control of metastatic disease that could cause morbidity becomes even more important.

In patients with long anticipated life expectancies as indicated by (1) oligometastatic disease and/or (2) a prognostic algorithm estimating a median life expectancy greater than 12 months, hypofractionated radiation therapy / stereotactic body radiation therapy (SBRT), a technique that conforms very closely to the target, thereby enabling high target doses and minimizing dose to normal surrounding tissue, can be a useful tool. Multiple publications looking at SBRT in oligometastatic disease have shown promising outcomes. These studies have treated oligometastatic sites throughout the body including lung, liver, lymph node and bone metastases. Among these patients with long overall survival (median survival of approximately 24 months), good local control (approximately 75% at 2 years) and low rates of toxicity (<10% risk of grade 3 toxicity) have been reported.^{7,8}

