2.3 Secondary Objectives

1. To assess patient reported quality of life, symptom control, and satisfaction with treatment using a modified version of the MD Anderson Symptom Inventory (MDASI)
2. To assess the rate of acute and chronic toxicity (e.g., fracture, myelopathy, radiculopathy)
3. To determine the median time to local failure, 1-year local progression-free survival, 1 year progression-free survival and 1-year overall survival in both cohorts.
4. To determine the 6-month local control rates, median time to local failure, 1-year local progression-free survival, and 1-year overall survival of patients in both cohorts, evaluated together.

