6.9 Radiation Adverse Events

6.9.1 All participants will be seen weekly by their treating radiation oncologist while undergoing therapy. The specific symptoms/side effects to be assessed will depend on the area(s) of the body undergoing treatment. A comprehensive list is below (see section 6.9.2); however every patient will not be assessed for every symptom if it is not relevant to the site(s) being treated.

Every patient will be assessed for:

- Pain – at the site(s) being treated
- Pain – at other locations
- Tiredness
- Skin reddening or irritation

- Skin peeling
- Nausea/Vomiting
- Hair loss

6.9.2 Comprehensive list of possible toxicities. The anticipated toxicity for each individual patient is very dependent on the location and the anticipated toxicities will be discussed in detail with the patient. These are listed in both the standard consent form the patient will sign for radiation treatment and the protocol-specific consent form as well as below.

Short Term Reactions (Appearing during radiation therapy or within 1 month thereafter; temporary, generally resolving within 2-3 months):

Common (> 20%):

- Tiredness
- Skin reddening & irritation that is reversible
- Loss of hair in the area of treatment
- Loss of taste
- Mild sore throat and difficulty swallowing
- Decreased blood counts that are reversible
- Weight loss that is reversible
- Pain flare

Rare (< 5%):

- Nausea
- Diarrhea
- Bladder irritation
- Fever and chills (within the first few hours of radiation)
- Severe esophagitis

Long Term Reactions (Appearing months after radiation; permanent, does not resolve)

Uncommon (10-20%):

- Mild scarring of skin or muscle without changes in function
- Mild scarring of the lung not requiring treatment
- Bone fractures

Rare (< 5%):

- Loss of hair in the treatment area
- Damage to spinal cord or nerves resulting in pain or other sensory changes
- Damage to spinal cord or nerves resulting in loss of motor function

- Damage to the esophagus limiting function

Extremely Rare ($\leq 1\%$):

- Tumors caused by radiation
- Damage to bone or muscle limiting function
- Sterility
- Damage to the heart

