13.2 Sample Size, Accrual Rate and Study Duration

We planned to enroll a total of 100 patients, 50 per cohort, into this study in the original design. As the accrual was rapid and about half of the patients were prostate cancer patients in cohort 1, the sample size for cohort 1 was increased from 50 to 100 to allow patients with other histologies to participate in this trial.

The primary endpoint is local control rate at 6 months. Assuming a cumulative incidence of local failure at 6 months is 10%, the 6-month local control rate is 90% with 90% exact binomial confidence intervals of [83.6%, 94.5%] and [80.1%, 96.0%] for cohorts 1 and 2, respectively. The confidence intervals are narrow enough to provide a precise estimate local control rate. With the sample size increase in cohort 1, we can also estimate the local control rates with better precision for the subsets of patients with either prostate cancer or other histologies. To be conservative, unevaluable patients (patients without valid assessments demonstrating free of local failure at 6 months) will be considered as failures in the analysis although we do not

anticipate many unevaluable patients on this study.

Approximately 250 patients per year are treated with conventional external beam radiation therapy for bone metastases in our department, with approximately one third being spine metastases. We estimate that approximately 10% of those 250 would be eligible for this study, yielding about 2 patients per month. Additionally, we are currently treating an average of 4 patients per month with SBRT for spinal metastases (75% eligible for cohort 1 and 25% eligible for cohort 2). It is expected that 70% of these patients will participate. Hence, we anticipate to accrue 3 and 1-2 patients per month for cohorts 1 and 2, respectively, and the accrual will be completed, in total for both cohorts, over about 3 years.

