13.6 Analysis of Secondary Endpoints

Secondary endpoints include, in each cohort, local progression-free survival (LPFS), progression-free survival (PFS), overall survival (OS) and patient reported quality of life (QOL) using the modified MD Anderson Symptom Inventory (MDASI).

LPFS is defined as the time from registration to local disease progression or death, whichever occurs first. PFS is defined as the time from registration to disease progression or death, whichever occurs first. Patients alive without documented progression will be censored at the date of last disease assessment. OS is defined as the time from registration to death or the date last known alive. Kaplan-Meier estimates will be used to describe event-time distributions.

Patient reported QOL, symptoms and satisfaction will be assessed using the modified MDASI general questionnaire and spine inventory at baseline, during treatment and all follow-up visits. The distributions of mean core symptom severity and mean interference score over time will be reported. The mean symptom severity of spine tumor will also be reported for patients with a spine site being treated on this study. The primary analysis for the QOL study is to evaluate the change in QOL from baseline to 3 months in this patient population using Wilcoxon signed rank test. Assuming 80% of patients complete the baseline and 3-month QOL assessments and a two-sided test with alpha=0.05, the study will have about 89% power to detect a difference of 0.3 standard deviation among all patients. All patients who receive at least one fraction of SBRT will

be monitored for toxicity, and the percent of patients with various toxicities will be tabulated for each cohort. The acute and chronic toxicity rates will also be reported. The probability of observing one or more toxicities with a true rate of 5% is 99.4% and 92.3% for cohort 1 and cohort 2, respectively.

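### Section 13.6 names no time-based estimator for chronic toxicity, so on its natural reading late events are understated when follow-up is incomplete, and the 99.4% and 92.3% detection figures need a label

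*Combined protocol and SAP*

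**What the plan says.** The secondary objective in Section 2.3 is "To assess the rate of acute and chronic toxicity (e.g., fracture, myelopathy, radiculopathy"). Section 6.9.2 puts bone fractures (10-20%) and spinal cord or nerve damage (under 5%) under "Long Term Reactions (Appearing months after radiation; permanent, does not resolve").

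Section 13.6 takes as its toxicity population everyone who receives at least one fraction. In that group, "the percent of patients with various toxicities will be tabulated for each cohort". A further sentence says only that acute and chronic rates will also be reported. It gives no denominator, time point, onset window, confidence interval, or rule for death and loss to follow-up. Kaplan-Meier estimation is mentioned after the definitions of LPFS, PFS and OS and is not tied to toxicity.

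The same section then states: "The probability of observing one or more toxicities with a true rate of 5% is 99.4% and 92.3" per cent, for cohorts 1 and 2 respectively. Acute and late events are not separated.

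On cohort size, Section 13.2 says "We planned to enroll a total of 100 patients, 50 per cohort", and later that "the sample size for cohort 1 was increased from 50 to 100". Accrual is expected to take about 3 years. Toxicity is scheduled at months 3 and 6, every 6 months through year 2, and annually in years 3 to 5 (Section 11.2.5). Patients lost to follow-up come off study (Section 5.6).

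**The concern.** A simple percentage works for acute toxicity, because almost every treated patient is observed through the short risk period. Late events are different. A patient enrolled near the end of a 3-year accrual, or lost at month 8, has not been observed through the months when a fracture or nerve injury could occur, yet stays in the denominator as event-free. The percentage then depends on when the data are cut and how many patients were lost. It also has no stated horizon.

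Nothing in the plan prevents an early cut. Section 15 refers to Section 13.2 for when outcome data are mature, but Section 13.2 sets no follow-up requirement. The primary endpoint is read at 6 months, so a first report about 6 months after the last entry is plausible.

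At stake is how late toxicity is described, above all in the 50-patient re-irradiation cohort, where Section 1.1.3 identifies cord injury as the main hazard. A reader could also take 92.3% as the chance of seeing a 5% late injury in that cohort, which holds only if all 50 patients can be observed for it.

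**Working it through.** **1. The plan's detection figures.** Inputs: n = 100 and 50 (Section 13.2), true rate 5% (Section 13.6). The chance of at least one event is 1 − 0.95^n.
- Cohort 1: 1 − 0.95^100 = 0.994.
- Cohort 2: 1 − 0.95^50 = 0.923.

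Both figures are reproduced. They use the full cohorts.

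**2. The same formula with fewer patients at risk.** The documents give no at-risk fraction for late toxicity, so these fractions are assumptions.

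| Fraction at risk | Cohort 1 (n) | Cohort 2 (n) |
|---|---|---|
| 100% | 99.4% (100) | 92.3% (50) |
| 80% | 98.3% (80) | 87.1% (40) |
| 50% | 92.3% (50) | 72.3% (25) |

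For orientation, Section 1.1.2 cites "long overall survival (median survival of approximately 24 months") for oligometastatic series. With exponential survival, that median leaves 50% alive at month 24.

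A gentler version lets patients have events before they die. Take a 5% net risk spread evenly over 24 months with a 24-month median:
- event hazard λ = −ln(0.95)/24 = 0.00214; death hazard μ = ln 2/24 = 0.0289;
- probability per treated patient = λ/(λ+μ) × (1 − e^(−24(λ+μ))) = 0.036;
- detection = 1 − (1 − 0.0362)^n = 97.5% (n = 100) and 84.2% (n = 50).

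**3. Crude percentage against cumulative incidence.** Assumptions not in the documents: 15% net risk by month 24, constant hazard from month 3 and continuing at that level; exponential death with a 24-month median; data cut 6 months after last entry; 1% monthly loss. From the plan: 36 months of accrual, taken as uniform, so possible follow-up F runs evenly from 6 to 42 months.
- λ = −ln(0.85)/21 = 0.00774; μ = 0.02888; loss ν = 0.01.
- Cumulative incidence at 24 months, death competing: e^(−3μ) × λ/(λ+μ) × (1 − e^(−21(λ+μ))) = 0.917 × 0.2113 × 0.5365 = 0.104.
- Crude percentage, with s = λ+μ+ν = 0.04662: e^(−3(μ+ν)) × λ/s × [1 − (e^(−3s) − e^(−39s))/(36s)] = 0.8899 × 0.1660 × 0.5787 = 0.0855.

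So the table would show about 8.5% (simulation runs give 8.5% to 8.6%) where the 24-month cumulative incidence is 10.4%. The gap is about 1.9 points, or about 18% in relative terms.

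**4. What drives the gap.**
- No loss, same early cut (ν = 0): 0.917 × 0.2113 × 0.5022 = 0.097, so 9.7% against 10.4%.
- No loss, every patient followed to month 24 or death, events counted to month 24: the crude percentage equals the cumulative incidence, 10.4%.

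The gap therefore comes from loss and early cut-off. Deaths do not produce it.

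**The case against.** Several points on the other side are sound.

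- **The text is not explicit.** Nowhere does Section 13.6 say that chronic toxicity is a percentage of all treated patients. That is the natural reading of the only method given, but the chronic rate has its own sentence and is simply undefined. The gap is a missing specification, and the remedy is the same on either reading.
- **Deaths.** A reader might infer that counting the dead as event-free biases the percentage. It does not, if the target is cumulative incidence with death as a competing event, because that quantity treats deaths in the same way. Only the risk among survivors would be understated.
- **Complete follow-up.** Toxicity is scheduled to year 5, and Section 15 allows reporting after the last data items are in. If follow-up is complete, the understatement disappears.
- **The detection figures.** A reader might infer that 99.4% and 92.3% are wrong. They are right if 5% is the event rate per treated patient, and the text makes no claim about late events.
- **Survival in cohort 1.** It is tempting to use the statement "In studies evaluating all patients with bone metastases, the median survival is approximately 9 months" for both cohorts. Section 1.1.2 contrasts that figure with the longer survival of oligometastatic patients, so it does not fit cohort 1. With a 24-month median, cohort 1 detection stays at about 97% over a 24-month risk period in the gentler version in step 2.
- **Size.** A 1.9-point gap is below the sampling standard error at a 10% rate: √(0.1 × 0.9/100) = 3.0 points for cohort 1 and √(0.1 × 0.9/50) = 4.2 for cohort 2. Toxicity is descriptive, and sample size rests on confidence-interval width for local control.

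These points limit the size of the concern. They do not supply the missing estimator, horizon or censoring rule.

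**Conclusion.** The point holds as a gap in specification with a cheap improvement available. Section 13.6 offers only a percentage of treated patients, with no time-based estimator for chronic toxicity, although the named events are late and observation time will be unequal. Read naturally, that percentage understates cumulative incidence when follow-up is incomplete: about 8.5% against 10.4% in the illustration, and no difference when everyone is followed to the horizon. That size rests on the assumed risk, data cut, loss rate and survival, none of which the plan states for toxicity. It should not be quoted as a forecast.

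The 99.4% and 92.3% stand as written for a 5% rate per treated patient with all patients observable. For a 5% risk among patients still at risk they are upper bounds. The shortfall is small in cohort 1 unless about half or more are no longer at risk, and larger in cohort 2. The documents do not support saying that late toxicity will be understated in all cases, or that the detection figures are in error.

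**What to change.** In Section 13.6:

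1. Keep the percentage table for acute toxicity, and state the acute and chronic windows. Section 6.9.2 already describes short-term reactions as arising up to 1 month after treatment and could be cross-referenced.
2. For chronic toxicity, report cumulative incidence at 6, 12 and 24 months in each cohort (Aalen-Johansen estimator), with death as a competing event, censoring at the last toxicity assessment, confidence intervals and numbers at risk.
3. Label 99.4% and 92.3% as applying to a 5% event rate per treated patient with all patients observable. Add that for a 5% risk among patients still at risk they are upper bounds, with the 80% and 50% rows above as examples and the fractions marked as assumptions.

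The cost is a few sentences and one standard estimator. Toxicity is already assessed at the visits needed, so no extra patients or visits are required; each late event needs an onset date, or the date of the assessment that first recorded it. The downside is a little more analysis work and slightly less favourable late-toxicity and detection figures.

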14. REGULATORY CONSIDERATIONS

14.1 Data Safety Monitoring

The DF/HCC Data and Safety Monitoring Committee (DSMC) will review and monitor toxicity and accrual data from this study. The committee is composed of clinical specialists with experience in oncology and who have no direct relationship with the study. Information that raises any questions about participant safety will be addressed with the Overall PI and study team.

The DSMC will review each protocol up to four times a year or more often if required to review toxicity and accrual data. Information to be provided to the committee may include: up-to-date participant accrual; current dose level information; dose-limiting toxicity information; all grade 2 or higher unexpected adverse events that have been reported; summary of all deaths occurring with 30 days of intervention for Phase I or II protocols; any response information; audit results, and a summary provided by the study team. Other information (e.g., scans, laboratory values) will be provided upon request.

14.2 Multicenter Guidelines

N/A

14.3 COLLABORATIVE AGREEMENTS LANGUAGE

N/A

APPENDIX A

PERFORMANCE STATUS CRITERIA

ECOG Performance Status Scale		Karnofsky Performance Scale	
Grade	Descriptions	Percent	Description
0	Normal activity. Fully active, able to carry on all pre-disease performance without restriction.	100	Normal, no complaints, no evidence of disease.
		90	Able to carry on normal activity; minor signs or symptoms of disease.
1	Symptoms, but ambulatory. Restricted in physically strenuous activity, but ambulatory and able to carry out work of a light or sedentary nature (e.g., light housework, office work).	80	Normal activity with effort; some signs or symptoms of disease.
		70	Cares for self, unable to carry on normal activity or to do active work.
2	In bed <50% of the time. Ambulatory and capable of all self-care, but unable to carry out any work activities. Up and about more than 50% of waking hours.	60	Requires occasional assistance, but is able to care for most of his/her needs.
		50	Requires considerable assistance and frequent medical care.
3	In bed >50% of the time. Capable of only limited self-care, confined to bed or chair more than 50% of waking hours.	40	Disabled, requires special care and assistance.
		30	Severely disabled, hospitalization indicated. Death not imminent.
4	100% bedridden. Completely disabled. Cannot carry on any self-care. Totally confined to bed or chair.	20	Very sick, hospitalization indicated. Death not imminent.
		10	Moribund, fatal processes progressing rapidly.
5	Dead.	0	Dead.

APPENDIX B STUDY PARAMETERS

Assessments	Pre-Study	Simulation	Radiation Treatment	Follow-Up ⁽¹⁾
Informed Consent and Registration	X			
History/physical/vital signs	X			X
Performance Status	X			X
Pregnancy Test (B-HCG)	X			
Diagnostic CT or MRI (at discretion of treating physician)		X ⁽²⁾		
Imaging study (CT or MRI to be determined by treating physician)				X ⁽³⁾
Toxicity Assessment	X		X ⁽⁶⁾	X
QOL questionnaire	X		X ⁽⁴⁾	X ⁽⁵⁾

- (1) Follow up schedule: initial evaluation at 1 week after completion of radiation therapy (via telephone, in person or email), then at 1 month after completion (via telephone, in person or email), 3 months, 6 months and every 6 months thereafter through year 2 (in person, telephone or email), then annually through year 5. Visits can be scheduled within a pre-specified time window around the anticipated date.
- (2) Baseline imaging is to be done within 21 days of start of first fraction of radiation
- (3) Follow up imaging is to be done within 2 weeks before or after scheduled follow up visit.
- (4) On mid-point and last day of radiation
- (5) QOL questionnaire to be completed within 2 weeks of follow up visit.
- (6) During on treatment visit

APPENDIX C ADVERSE EVENT REPORTING REQUIREMENTS

DEFINITIONS:

Adverse Event (AE)

An adverse event (AE) is any undesirable sign, symptom or medical condition or experience that develops or worsens in severity after starting the first dose of study treatment or any procedure specified in the protocol, even if the event is not considered to be related to the study.

Abnormal laboratory values or diagnostic test results constitute adverse events only if they induce clinical signs or symptoms or require treatment or further diagnostic tests.

Serious adverse event (SAE)

A serious adverse event (SAE) is any adverse event, occurring at any dose and regardless of causality that:

- Results in death
- Is life-threatening. Life-threatening means that the person was at immediate risk of death from the reaction as it occurred, i.e., it does not include a reaction which hypothetically might have caused death had it occurred in a more severe form.
- Requires or prolongs inpatient hospitalization (i.e., the event required at least a 24-hour hospitalization or prolonged a hospitalization beyond the expected length of stay). Hospitalization admissions and/or surgical operations scheduled to occur during the study period, but planned prior to study entry, are not considered SAEs if the illness or disease existed before the person was enrolled in the trial, provided that it did not deteriorate in an unexpected manner during the trial (e.g., surgery performed earlier than planned).
- Results in persistent or significant disability/incapacity. Disability is defined as a substantial disruption of a person's ability to conduct normal life functions.
- Is a congenital anomaly or birth defect; or
- Is an important medical event when, based upon appropriate medical judgment, it may jeopardize the participant and require medical or surgical intervention to prevent one of the outcomes listed above. Examples of such medical events include allergic bronchospasm requiring intensive treatment in an emergency room or at home; blood dyscrasias or convulsions that do not result in inpatient hospitalization, or the development of drug dependency or drug abuse.

Events **not** considered to be serious adverse events are hospitalizations for:

- routine treatment or monitoring of the studied indication, not associated with any deterioration in condition, or for elective procedures
- elective or pre-planned treatment for a pre-existing condition that did not worsen
- emergency outpatient treatment for an event not fulfilling the serious criteria outlined above and not resulting in inpatient admission
- respite care

Expectedness: Adverse events can be 'Expected' or 'Unexpected.'

- Expected adverse event
 - Expected adverse events are those that have been previously identified as resulting from administration of the agent. For the purposes of this study, an adverse event is considered expected when it appears in the current adverse event list or is included in the informed consent document as a potential risk.
 - Refer to Section 6.9 for a listing of expected adverse events associated with the study agent.
- Unexpected adverse event
 - For the purposes of this study, an adverse event is considered unexpected when it varies in nature, intensity or frequency from information provided in the current adverse event list or when it is not included in the informed consent document as a potential risk.

Attribution

- Attribution is the relationship between an adverse event or serious adverse event and the study treatment. Attribution will be assigned as follows:
 - Definite – The AE is clearly related to the study treatment.
 - Probable – The AE is likely related to the study treatment.
 - Possible – The AE may be related to the study treatment.
 - Unlikely - The AE is doubtfully related to the study treatment.
 - Unrelated - The AE is clearly NOT related to the study treatment.

PROCEDURES FOR AE AND SAE RECORDING AND REPORTING

Investigators will assess the occurrence of AEs and SAEs at all participant evaluation time points during the study.

All AEs and SAEs whether reported by the participant, discovered during questioning, directly observed, or detected by physical examination, laboratory test or other means, will be recorded in the participant's medical record and on the appropriate study-specific case report forms.

The descriptions and grading scales found in the CTEP Active Version of the NCI Common Terminology Criteria for Adverse Events (CTCAE) will be utilized for AE reporting. The CTEP Active Version of the CTCAE is identified and located on the CTEP website at:

http://ctep.cancer.gov/protocolDevelopment/electronic_applications/ctc.htm.

All appropriate treatment areas should have access to a copy of the CTEP Active Version of CTCAE.

ADVERSE EVENT REPORTING REQUIREMENTS

Serious Adverse Event Reporting

All serious adverse events that occur after the initial dose of study treatment, during treatment, or within 30 days of the last dose of treatment must be reported to the DF/HCC Overall Principal Investigator on the local institutional SAE form. This includes events meeting the criteria outlined in Serious Adverse Event (as above), as well as the following:

- Grade 2 (moderate) and Grade 3 (severe) events that are unexpected and at least possibly related/associated with the intervention.
- All Grade 4 (life-threatening or disabling) events that are unexpected or not specifically listed in the protocol as not requiring reporting.
- All Grade 5 (fatal) events while the participant is enrolled and actively participating in the trial OR when the event occurs within 30 days of the last study intervention.

Note: If the participant is in long term follow up, report the death at the time of continuing review.

Participating investigators must report each serious adverse event to the DF/HCC Overall Principal Investigator within 24 business hours of learning of the occurrence. In the event that the participating investigator does not become aware of the serious adverse event immediately (e.g., participant sought treatment elsewhere), the participating investigator is to report the event within 24 hours after learning of it and document the time of his or her first awareness of the adverse event. Report serious adverse events by telephone, email or facsimile to:

[name] MPH
[contact] or [contact]
[contact]

Within the following 24-48 business hours, the participating investigator must provide follow-up information on the serious adverse event. Follow-up information should describe whether the event has resolved or continues, if and how the event was treated, and whether the participant will continue or discontinue study participation.

Non-Serious Adverse Event Reporting

Non-serious adverse events will be reported to the DF/HCC Overall Principal Investigator on the toxicity Case Report Forms.

Reporting to the study sponsor: N/A

Reporting to the Institutional Review Board (IRB)

Investigative sites within DF/HCC will report all serious adverse events directly to the DFCI Office for Human Research Studies (OHRS).

Reporting to the Food and Drug Administration (FDA): N/A

Reporting to the NIH Office of Biotechnology Activities (OBA): N/A

Reporting to the Institutional Biosafety Committee (IBC): N/A

Reporting to Hospital Risk Management

Participating investigators will report to their local Risk Management office any subject safety reports or sentinel events that require reporting according to institutional policy.

MONITORING OF ADVERSE EVENTS AND PERIOD OF OBSERVATION

All adverse events, both serious and non-serious, and deaths that are encountered from initiation of study intervention through the study intervention period and up to 30 days after the last study intervention should be followed to their resolution, or until the participating investigator assesses them as stable, or the participating investigator determines the event to be irreversible, or the participant is lost to follow-up. The presence and resolution of AEs and SAEs (with dates) should be documented on the appropriate case report form and recorded in the participant's medical record to facilitate source data verification.

For some SAEs, the study sponsor or designee may follow-up by telephone, fax, and/or monitoring visit to obtain additional case details deemed necessary to appropriately evaluate the SAE report (e.g., hospital discharge summary, consultant report, or autopsy report).

Participants should be instructed to report any serious post-study event(s) that might reasonably be related to participation in this study. Participating investigators should notify the DF/HCC Overall Principal Investigator of any unanticipated death or adverse event occurring after a participant has discontinued or terminated study participation that may reasonably be related to the study.

